10.3.4 Data user/consumers spreadsheet: Breast Cancer Specialist and CVD clinicians

Breast Cancer

Form to be used by the Breast Cancer Specialist to enter time related to management of the BC registry

Breast Cancer Specialist - Data User Form - G0	
Site name:	 NEMC - Sihtasutus Põhja-Eesti Regionaalhaigla UM - Maastricht University MUG - Medizinische Universität Graz
Data User ID / pseudonym:	✓
To be computed for 45 patients across sites (15 patients in your own site + time to get info on 30 patients in t	he other 2 sites)
TBC1. Estimated time to compute the percentage of patients - across sites - treated with breast conserving therapy and whole breast radiotherapy that receive a boost to the tumour bed without AIDAVA (in min):	(example: 2 or 6 or)
TBC2. Estimated time to compute the number of patients - across sites - undergoing surgery and radiotherapy, without adjuvant chemotherapy: % of patients with time between surgery and radiotherapy > 8 weeks without AIDAVA (in min):	(example: 2 or 6 or)
TBC3. Estimated time to compute the number of patients - across sites - receiving radiotherapy: Percentage of patients receiving any nodal radiotherapy without AIDAVA (in min):	(example: 2 or 6 or)

This form is linked with a table that contains all the metrics manually entered in REDCap (as .csv-export) that are needed to evaluate the system from a BC specialist perspective.

Breast			G1				G2	
Cancer	BC1	BC2	BC3	Comments	BC1	BC2	BC3	Comments
NEMC								
MUG								
Maastro								
MEAN								
MEDIAN								

CVD specialist

Form to be used by the CVD specialist to enter the manually computed SMArt score and the time needed to compute this form manually

CVD Specialist - Data User Form - G1 & G2	
Generation of the prototype	 B O Generation 1 C Generation 2 reset
Site name:	 NEMC - Sihtasutus Põhja-Eesti Regionaalhaigla UM - Maastricht University MUG - Medizinische Universität Graz
Data User ID / pseudonym:	~
Patient ID / pseudonym:	
Date:	H Today Y-M-D
CVD1. SMART risk score computed by the physician(s) for the patient (from this site): U-prevent SMART risk score calculator	SMART risk score computed by CVD Specialist SMART risk score computed by another person Name of this other person
TCVD1. Time required for the treating physician to compute the SMART risk score (collect + analyze + enter data into a standalone web page calculator) in min:	(example: 10 or 20 or)
How useful was the patient status graphical display (with balloons)	
- to assess the status of the patient:	(scale 1 to 5)
- to communicate with the patient on their status:	(scale 1 to 5)
Please enter any comments related to the graphical display:	(free text)

This form is linked with a table that contains all the metrics manually entered in REDCap (as .csv-export) that are needed to evaluate the system from a CVD specialist perspective.

CVD		G1			G1				
	CVD1	TCVD1		Comments		CVD2	TCVD2		Comments
NEMC									
MUG									
UMUC									
MEAN									
MEDIAN									

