3.2.2 Cardiovascular Use case

Objective. The objective of the endpoints below is to demonstrate the value of having interoperable and reusable data in a standard format to generate valuable and high-quality information in clinical care, without additional burden to the treating physicians.

Objective	(Secondary) end point
Metric 1. Compare scoring time	Metric definition: Time to compute the SMART score (see
between AIDAVA and CVD	definition below)
expert	
	Measurement:

Objective	(Secondary) end point	
	TCVD. Time required for the treating physician to compute the SMART risk score (collect + analyse + enter data into a standalone web page calculator) - per estimate of user in dedicated entry form - compared to the time needed to calculate the same score by AIDAVA, automatically (G1 and G2)	
Metric 2: Compare scoring accuracy between AIDAVA and CVD expert	Metric definition: Accuracy of automatic calculation of the U-Prevent SMART risk score compared to cardiovascular expert-entered score calculation (% difference in the score output - per estimate of user in dedicated entry form) (G1 and G2)	
	 Measurement: CVD1. U-Prevent SMART score computed by treating physician (https://u-prevent.com/calculators/smartScore) CVD2. U-Prevent SMART score computed by AIDAVA 	

The SMART Risk Score [4] is a tool to estimate 10-year risk for recurrent vascular events in patients with manifest cardiovascular disease. The calculator is located at the U-Prevent site [5], a clinical decision support platform, for the application of risk prediction models in clinical practice; the calculator has been recreated and optimised by ORTEC for personalised cardiovascular risk management. The U-Prevent site is CE marked according to the Medical Devices Directives (MDD); marking for MDR compliance is in progress. The pilot site was built by UMC Utrecht. Using the calculators is free. The U-Prevent team develops extra services for premium users, optimization of data management, e.g. by FAIR and GDPR-compliant data exchange from electronic health records. Technical specification to compute Model A, the SMART Risk Score [6] can be found below.

Formulas	SNOMED / LOINC Code (available in PHKG)	Population ¹² value if missing
Recalibrated SMART risk score for	patients with CVD:	
10-year cardiovascular disease risk	: (%) = (1- 0.71840 exp[A + 1.933]) x 100%	
where A =		
-0.0349602236 x age in years	Compute from SNOMED: 184099003 Date of birth	Mandatory

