The senior physician will then be able to decide on one of the following reasons for discrepancy. Health record incomplete: the information was not available in the medical record, while it should have been – and therefore AIDAVA could not identify the right value.

- Error in AIDAVA: the information is rightly included in the medical record, but AIDAVA did not include this information properly
- Error from physician: AIDAVA is right and the junior physician evaluation is not correct.

To assess the longitudinal aspects of AIDAVA, the SMART score will be calculated 2 times (after G1 and \pm 16 to 18 months later, at the end of G2 use year follow-up). The aim is to see if modifiable risk factors can be captured and risk can be calculated by AIDAVA automatically and reliably.

4. Study Design

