SDPO	GO	With ± 15 patients on site	 EBCx: estimated total effort (person min, person hours or person days) for BC specialist and supporting local team to answer the queries (BC1, BC2, BC3 described in Section 3.2.1) across sites TBCx: estimated duration (min, hours or days) for the BC specialist to have an answer to the queries (BC1, BC2, BC3) across sites. Duration = time between the first request and the time the answer is provider 		
SDP1	G1	All patients	 EBCx: total effort for BC specialist (and local team) to answer the queries (BC1, BC2, BC3) across sites TBCx: duration (min, hours or days) for the BC specialist to have an answer to the queries (BC1, BC2, BC3) across sites. HBCx: answer to the query as provided by human BC specialist ABCx: answer to the query as computed by AIDAVA ACCx: accuracy of calculation by AIDAVA compared to BC specialist 		
SDP2	G2		Same than SDP1 - for G2		
		1	CVD		
SDP1	G1	All patients	 CVD. SMART risk score computed by AIDAVA TCVD1.1/TCVD1.2. Time required for the treating/ senior physician to compute the SMART score (collect + analyse + enter data into a standalone web page calculator) CVD1.1/CVD1.2. SMART score computed by treating / senior physician ACVD1.1/ACVD1.2. Accuracy of automatic calculation of the score compared to treating/senior physician-entered score 		
SDP2	G2		Same than SDP1 - for G2		

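### The CVD data-user form has no designated field for the senior physician's time or the discrepancy reason, and its two scores are not labelled treating and senior as Section 9.2 requires

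*Protocol*

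**What the plan says.** Section 9.2 lists the CVD secondary data for G1 and repeats them for G2. Three items come in treating/senior pairs:

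- times: "TCVD1.1/TCVD1.2. Time required for the treating/ senior physician to compute the SMART score"
- scores: "CVD1.1/CVD1.2. SMART score computed by treating / senior physician"
- accuracies: "ACVD1.1/ACVD1.2. Accuracy of automatic calculation of the score compared to treating/senior physician-entered score"

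Section 3.2.2 has the score computed by AIDAVA and by the treating (junior) physician, and then checked by the senior physician. Where they differ, "The senior physician will then be able to decide on one of the following reasons for discrepancy". The three reasons are an incomplete record, an error in AIDAVA, and an error by the physician with AIDAVA right.

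The CVD Specialist Data User Form for G1 and G2 (Section 10.3.4; Form 14 in the Schedule of Activities) has one time field: "TCVD1. Time required for the treating physician to compute the SMART risk score (collect + analyze + enter data". It has two score fields, one for the CVD specialist and one for "SMART risk score computed by another person", followed by that person's name. Its only free text concerns the graphical display. The linked export table, described as holding the metrics "needed to evaluate the system from a CVD specialist perspective", has columns CVD1 and TCVD1, then CVD2 and TCVD2, with both halves headed G1. In Section 3.2.2 the label is already taken: "CVD2. U-Prevent SMART score computed by AIDAVA".

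**The concern.** The analysis set names variables that the collection form does not provide for. If sites fill in the form as printed, the senior physician's time has nowhere to go. An analyst would also have to guess which recorded score is the treating physician's and which is the senior's. The reason code is the protocol's only explicit means of separating AIDAVA error, physician error and incomplete source records, and it too has no place on the form.

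This cannot be left to an analysis plan, because an analysis plan cannot restore a role label or an adjudication that was not written down. The deliverable's own section on REDCap data collection says that everything needed for the endpoints must be captured in a similar way across sites. Section 4.4 provides for deleting patient data and the PHKG after the evaluation report, while the End-of-Study section keeps the PHKG to the end of the project. After deletion, re-adjudication from source in AIDAVA would no longer be possible.

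**Working it through.** The plan states no figure to reproduce here. The check sets required items against printed fields.

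| Item, per patient and generation | Required (9.2; 3.2.2) | Designated on the printed CVD form |
|---|---|---|
| Physician time | 2 (treating, senior) | 1, worded for the treating physician |
| Physician score | 2 (treating, senior) | 2, but labelled CVD specialist and another person |
| Discrepancy reason | 1, where scores differ | 0 |

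**Can the roles be recovered elsewhere?** The form records a Data User ID and the other person's name, so the people can be identified. The site participant list registers CVD specialists 1 and 2 without seniority. Identity is therefore captured, but the treating/senior role is not.

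**Does another form hold the missing items?**

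- Section 4.4 sends the score result and time to the Patient Monitoring form. As printed, that form has a yes/no item on whether the score was available and viewed, plus general comments. It has no score, time or reason field.
- Section 3.2 says secondary endpoints go into a spreadsheet modelled in Section 10.6. As shown, Section 10.6 is the SMART score code and contains no such model.

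**Does the linked table settle it?** The second half could mean G2 physician entries, senior-physician entries or AIDAVA's values. The parallel breast cancer table is headed G1 and G2, so a slip for G2 is the likeliest reading. On that reading CVD2 would be a physician score, against its meaning in Section 3.2.2. Section 9.2 calls AIDAVA's score simply CVD, so the naming is unsettled in any case.

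**Extent.** There are 15 × 3 = 45 planned CVD patients. With one completed form per generation and full numbers at both, that is 45 × 2 = 90 values of TCVD1.2 without a designated field.

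**Effect on accuracy.** ACVD1.1 compares AIDAVA with the treating physician. A treating-physician error therefore lowers it by definition, whatever the form holds. ACVD1.2 uses the senior score and need not be affected. The CVD hypothesis in Section 9.1 sets 80% or more, and Section 9.3 analyses time and accuracy without the treating/senior suffix. Neither says which member of each pair is meant.

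**The case against.** A fair defence runs as follows. Form 14 is keyed by data user, patient and generation, so a senior physician could file a second record under their own ID, and the export table has a TCVD2 column. The scorers are identifiable. The reason might be kept in a comments field, or in the adjudication screen, whose figure is not reproduced. Section 3.2.2 describes the senior physician as checking the score rather than timing a separate calculation. The reason is not an endpoint in Section 9.2, and the protocol is a template open to local adaptation.

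Much of this limits the point without removing it. A second record would contradict the wording of the time field, TCVD2 is undefined, and nothing printed designates a comments field for the reason. The text supports saying that there is no designated field.

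A reader might go further in three ways that the documents do not support:

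- **That TCVD1.2 will never be collected.** The second-record route remains open, so this cannot be asserted.
- **That the form causes physician errors to be charged to AIDAVA, with a calculable loss of the chance to meet 80%.** The charge to ACVD1.1 comes from its definition. No rule in Sections 9.1 to 9.3 uses the reason to correct either accuracy, so a reason field alone would change no result. Any probability would need invented error rates and an all-or-nothing agreement measure, whereas Section 3.2.2 defines accuracy as a percentage difference in the score. On that measure small input errors count little. With the printed coefficient, a 5 mmHg difference in systolic pressure moves the linear predictor by 5 × 0.0018913154 = 0.0095, a relative change in risk of at most about 1%.
- **That the study will compare physicians with physicians through columns CVD1 and CVD2.** No analysis in Section 9.3 uses those columns in that way.

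**Conclusion.** The mismatch between form and analysis set is real and worth correcting before data are collected. As printed, TCVD1.2 has no designated field, the two scores carry no treating/senior label, so ACVD1.1 and ACVD1.2 cannot be reliably separated, and the senior physician's adjudication has no designated place. It reaches every CVD patient at both generations: up to 90 patient-by-generation records, assuming 45 patients and one form each time. The reason applies only where scores differ.

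The size of any effect on reported accuracy is unknown. The documents give neither physician nor AIDAVA error rates, and none can be derived from them. The conclusion rests on the forms as printed and would weaken if the missing figure or a local version of the form records roles and reasons.

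**What to change.** - In Form 14, replace the present score and time fields by two labelled blocks: treating physician (CVD1.1, TCVD1.1) and senior physician (CVD1.2, TCVD1.2), each with the scorer's study ID.
- Add a coded discrepancy-reason field with the three categories of Section 3.2.2, mandatory when the scores differ.
- State how the reason is used: report ACVD as defined, and also with discrepancies adjudicated as physician error not counted against AIDAVA.
- Correct the second G1 heading in the linked table if G2 is meant, and keep CVD2 for AIDAVA's score as in Section 3.2.2.

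The cost is a REDCap edit and about two extra entries per patient and generation (at most 45 × 2 × 2 = 180 in all) by a physician who already does the check. As the form is printed in the protocol, the change may count as an amendment needing ethics approval under Section 11.1.

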10.4 Feedback to the patient

• Communication every 2 months

- **Objective**: provide regular information on the project to maintain interest the patient to decrease dropout during the G2 development/ improvement phase
- **Medium**: Regular newsletters (send through emails; additional online meetings after 9 months will be explored).
- Expected planning and content
 - Across all newsletters: in each communication include a message highlighting the advantages of using AIDAVA, key milestones and achievements in the project, the value of patients' participation in the evaluation, and the important steps the patients can take to improve the quality of care by using it.

Number	Time	Content
1	Oct 2024	Thank you - highlights from evaluation
2	Jan 2025	Comments from Ethical Advisory Board and data privacy aspects Comments Sustainability Advisory Board on potential development and future use of the application
3	Apr 2025	Perspective from Health Data Intermediaries on further extension and use of AIDAVA like tools. How does this fit in the wider perspective of EHDS
4	Jul 2025	Progress on development of G2 - how patients feedback was key to improving features for G2. What is coming in G2 and what we expect from patients and
5	Oct 2025	G2 is coming - confirmation of new features - we count on you to help evaluate this

• Proposed focus per newsletters

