4.4.3. Development of G2 (improvement of G1)

	CVD patients	BC patients
August 2024 /Sept	Development of G2 Patient will receive information letters of	every 3 months
2025	CVD Patients will continue using the Medical device (see Section 6) and will continue sending these data to Data Intermediary. In case of problems patient can contact the research associate	

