9.3 Statistical Analyses

Three tests have be retained

- **Paired t-test**: statistical test that compares the means of two related groups, where each subject is measured at two different time points or under two different conditions. It is used to determine if there is a significant difference between the two groups.
- Mann-Whitney U test (unpaired t-test): non-parametric statistical test used to compare the medians of two independent groups. It is often used when the data are not normally distributed or when the sample sizes are small.
- Wilcoxon signed-rank test: non-parametric statistical hypothesis test used to compare two populations with two matched samples.

Primary Endpoint(s) Analysis

The endpoints are defined in Section 9.2 will be used to support the analysis

Computed	Description of measures	Test & meaning (per H1)			
	Population: Expert Curators				
E1	Difference between data points 1 and 2: E1.M2.1△ = M2.1@PDP1 - M2.1@PDP2 E1.M2.2△ = M2.2@PDP1 - M2.2@PDP2	Paired t-test H1: less time spent in curation in G1 than in G0 for expert curators			
E2	Difference between data points 2 and 3: E2.M1-Δ = M1@PDP2 - M1@PDP3	Paired t-test H1: G2 is more usable than G1 for expert curators			
	E2.M2.1∆ = M2.1@PDP2 - M2.1@PDP3 E2.M2.2∆ = M2.2@PDP2 - M2.2@PDP3	H1: less time spent in curation in G2 than in G1 for expert curators			
	Population:	Patients			
P1	Difference in data points 4 and 5 (i.e. difference between G1 and G2 for arm where patients used G1 AND G2)	Paired t-test (effect of system + training/experience from G1)			
	P1.M1- = M1@PDP4 - M1@PDP5	H1: G2 more usable than G1			
	P1.M2.x∆ = M2.x@PDP4 - M2.x@PDP5	H1: G2 requires less time for curation than G1 H1: G2 enables curation with less human intervention than G1			
	P1.M3-∆ = M3@PDP4 - M3@PDP5	H1: G2 provide same or higher quality than G1			
P2	Difference in data points 6 and 7 (i.e. difference between G1 and G2 for arm where patients used G1 OR G2)	Unpaired t-test (effect of system only)			
	P2.M1- = M1@PDP6 - M1@PDP7	H1: G2 more usable than G1			
	P2.M2.x∆ = M2.x@PDP6 - M2.x@PDP7	H1: G2 requires less time for curation than G1 H1: G2 enable curation with less human intervention than G1			
	Ρ2.Μ3-Δ = M3@PDP6 - M3@PDP7	H1: G2 provide same or higher quality than G1			

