A1	Sum across patient arms for G1 A1.M1 = M1@PDP4 + M1@PDP6 A1.M2.x = M2.x@PDP4 + M2.x@PDP6 A1.M3.x = M3.x@PDP4 + M3.x@PDP6 A1.M4.x = M4.x@PDP4 + M4.x@PDP6	Descriptive Statistics Performance in G1 of the AIDAVA system.			
A2	Sum across patient arms for G2	Descriptive Statistics			

Computed	Description of measures	Test & meaning (per H1)
	A2.M1 = M1@PDP5 + M1@PDP7 A2.M2.x = M2.x@PDP5 + M2.x@PDP7 A2.M3.x = M3.x@PDP5 + M3.x@PDP7 A2.M4.x = M4.1@PDP5 + M4.x@PDP7	Performance in G2 of the AIDAVA system.
A3	Difference in A1 and A2 (i.e. difference between G1 and G2 across all patients)	Unpaired t-test
	Α3.Μ1-Δ = Α1.Μ1 - Α2.Μ1	H1: G2 more usable than G1
	A3.M2.xΔ = A1.M2.x - A2.M2.x A3.M3.x-Δ = A1.M3.x - A2.M3.x	H1: G2 requires less time for curation than G1 H1: G2 enable curation with less human intervention than G1
	A3.M4.X-∆ = A1.M4.x - A2.M4.x	Wilcoxon signed-rank test H1: The NLP system developed in G2 yields a higher precision than the NLP system from G1. H1: The NLP system developed in G2 yields a higher recall than the NLP system from G1.
A4	Difference in P1 and P2 (difference between the 2 patient arms)	Unpaired t-test (effect on training/experience) There is a difference in performance due to training/experience with the system : patients having used G1 are more/not more effective in G2 than patients who work with only one generation of the prototype (G1 or G2)
	Α4.Μ1-Δ = P1.Μ1-Δ - P2.Μ1-Δ	H1: G2 more usable than G1 (due to experience during G1)
	A4.M2.x-Δ = P1.M2.x-Δ - P2.M2.x-Δ A4.M3.x-Δ = P1.M3.x-Δ - P2.M3.x-Δ	H1: G2 requires less time for curation than G1 as patients are more experienced H1: There are less questions of the system unanswered during G2 than in G1 as the patient acquired experience in G1
	A4.M4	Not useful

Secondary Endpoint(s) Analysis

Description of measures	Test & meaning (per H1)
Breast Canc	er
Difference in data points 0 and 1 (i.e. difference between G0 and G1 across a sample of 15 patients) U0.TBCx- Δ = TBCx@SDP0 - TBCx@SDPA U0.EBCx- Δ = EBCx@SDP0 - EBCx@SDP1 U0.ACCx- Δ = ACCx@SDP0 - ACCx@SDP1	Unpaired t-test H1: G2 has more (or same) accuracy than G1 while keeping the same time saving and duration
	Descriptive Statistics around performance in G1 of the AIDAVA system (e.g. mean,)

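### Newsletters 4 and 5 tell enrolled patients that G2 has been improved before they rate it, and section 9.3 would read any effect of that message as training/experience (A4)

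*Protocol*

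**What the plan says.** Section 10.4 of the study protocol (Annex 1) schedules newsletters for October 2024 and January, April, July and October 2025. Their purpose is retention: "to decrease dropout during the G2 development/ improvement phase". Across all issues the rule is "in each communication include a message highlighting the advantages of using AIDAVA", and section 2.1.3 of the main report repeats it. The focus of issue 4 is "Progress on development of G2 - how patients feedback was key to improving features for G2". The focus of issue 5 is "G2 is coming - confirmation of new features - we count on you to help evaluate this". Section 4.4.3, on the G2 development period, says "Patient will receive information letters".

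Acceptance (M1) is one of four primary metrics. It is a self-completed System Usability Scale (SUS) with added questions, such as whether the user would recommend AIDAVA (sections 3.1 and 10.3.3).

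Section 9.3 labels the contrasts as follows:
- P1, patients who used both generations: "effect of system + training/experience from G1".
- P2, patients who used one generation: the effect of the system alone.
- A4 = P1 - P2: the effect of training/experience, with the M1 hypothesis "H1: G2 more usable than G1 (due to experience during G1").

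None of these labels mentions the newsletters.

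**The concern.** The patient arms let section 9.3 separate what the tool does from what prior experience with it does. That works only if experience is the one thing that returning patients have and single-generation patients lack. The newsletters are a second difference. Returning patients are told, before rating G2, that it contains improvements which they helped to bring about. The rating is an unblinded opinion, which such a message could shift.

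At stake is the reading of A4 for M1. A difference due partly or wholly to communication would be reported as a benefit of training, and that could misdirect decisions on how much training a later product needs. Every patient in the returning arm is sent the same material, so no later adjustment can separate the two effects.

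**Working it through.** **The plan's own figures.** The enrolment total reproduces: 15 patients x 3 sites x 2 use cases = 90. Section 9.4 gives no alpha, power, effect size or standard deviation, so there is no power figure to reproduce.

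**Who has seen what before rating.** The G1 evaluation runs July to September 2024 (section 4.1). The returning patients' G2 SUS is at Visit 3, Week 2 Day 5, March 2026 (section 4.4.4). New breast cancer patients for G2 enter at Visit 0, September 2025 to February 2026; new CVD patients enter on Week 1 Day 1 of the evaluation (section 4.4.2).

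| Rating | Group | Newsletters before the rating |
|---|---|---|
| G1 | all patients | none |
| G2 | returning | issues 1 to 5 |
| G2 | new CVD | none |
| G2 | new breast cancer | none, or issue 5 if enrolled around September-October 2025 |

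G1-only patients may get newsletters too, but only after their single rating.

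**What the contrasts contain.** Let s be the system effect, e the experience effect and m the messaging effect on the G2 rating. Write each gain as G2 minus G1; the protocol writes G1 minus G2, which only flips the sign. Assume the arms are otherwise alike and neglect the few new breast cancer patients who might see issue 5.
- P1 = s + e + m
- P2 = s
- A4 = P1 - P2 = e + m
- A3, all patients pooled, = s + w(e + m), where w is the share of G2 raters who are returning patients. If 70 return and 20 are new, w = 70/90 = 0.78; if 50 return and 40 are new, w = 50/90 = 0.56.

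A simulation with s = 0.30, e = 0.20 and m = 0.25 gave P1 = 0.750, P2 = 0.301 and A4 = 0.449. The true experience effect was 0.20, so A4 picks up the whole of m.

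**Illustration only.** The size of m cannot be derived from the documents. The values of m, the correlations, the arm sizes and the two-sided 5% level below are all assumptions, with no true system or experience effect.
- P1: rejection rate = Phi(m*sqrt(n) - 1.96) + Phi(-m*sqrt(n) - 1.96), with m in SDs of the paired difference. For m = 0.1 it is 11% (n = 50) to 15% (n = 80); for m = 0.2 it is 29% to 43%.
- A4: SE = sqrt(2(1 - rho)/n_returning + 1/n_G1only + 1/n_G2only), with m in SDs of the score. With 70/20/20 and rho = 0.3, SE = sqrt(0.02 + 0.05 + 0.05) = 0.346; with 50/40/40 and rho = 0.7, SE = sqrt(0.012 + 0.025 + 0.025) = 0.249. For m = 0.3 the rejection rate runs from 14% to 23%; for m = 0.5, from 30% to 52%.

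These rates are simply the power to detect an assumed shift. The 50 to 80 subjects in section 9.4 are the number judged sufficient for the study, not a count of returning patients. On the SUS scale, one response step on one item is worth 2.5 points (section 2.1.2 of the main report).

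**The case against.** The strongest reply has five parts.

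- **P2 is clean.** A reader might infer that no usability gain could be attributed to the tool. The documents do not support that: P2 is the contrast labelled as the system alone, and it is essentially unexposed. P1 is already declared a composite. This stands, and it narrows the problem to the experience label.
- **Benefit messages reach everyone.** Section 4.3 and training modules M1a and M1c (Annex 3) present expected benefits to every entrant before a first rating. This stands for the general line on advantages. It does not cover the G2-specific content of issues 4 and 5, which has no counterpart for new entrants.
- **Exposure and direction are inferred.** A reader might infer that returning patients alone receive the letters and that P1 is therefore biased toward G2. No distribution list is given, and new breast cancer patients enrolled around September-October 2025 might receive issue 5. Raised expectations could also lower ratings. Both limits stand.
- **The expectation is partly unavoidable.** Patients agree to test both generations (section 5.2), and returners have a 2.5-hour session on the G2 version before rating it (section 4.4.4). Neutral newsletters cannot hide that G2 is the later version. This stands, but it does not justify adding an avoidable message on top.
- **Retention matters.** Section 7.2 names discontinuation as a risk, and the patient consultants asked for newsletters on progress and on how AIDAVA can support patients. This argues for keeping the mailings. It does not require telling patients before the rating that G2 is improved. The 10.4 content is headed as expected and proposed, so it can still be changed.

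**Conclusion.** The point holds in a limited form. By the protocol's own calendar, the G2-specific messages of issues 4 and 5 fall between the two ratings for returning patients and miss nearly all new G2 patients. Any effect on M1, and possibly on M2.1, goes undiluted into P1 and A4, and in part into A3. Section 9.3 then assigns all of A4 to training/experience.

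The conclusion rests on two inferences: that letters go to patients already enrolled, which the retention purpose and the dates support, and that an unblinded opinion can respond to such a message. The magnitude is unknown, and no false-positive rate should be quoted as a property of this study.

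The scope is also limited. The system-computed M3 and M4 are essentially unaffected, and section 9.1 names M2 and M3, not M1, as the two critical metrics. This is a cheap improvement, not a defect that undermines the study.

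**What to change.** 1. In section 10.4, keep all five newsletters with thanks, milestones, dates and practical information. Reword issues 4 and 5 so that they do not say or imply that G2 is improved, and move that content to the Visit 4 feedback, after the Week 2 Day 5 SUS.
2. Preferably limit the line on advantages, in section 10.4 and in section 2.1.3 of the main report, to what new entrants are also told.
3. In section 9.3, state that A4 for M1, and the experience part of P1 for M1, may include communication effects. Rest the system-only usability conclusion on P2 for M1.

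The cost is rewording two one-page newsletters, one line in two places and a short note in section 9.3. The mailings may be slightly less engaging, and the expectation that comes from knowing G2 is the later version remains.
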